Rationale:	
Cryptococcal meningitis (CM) is a fungal infection that causes a severe syndrome of meningitis that is 100% fatal without antifungal therapy. Even with antifungal therapy, mortality rates remain high, especially in sub-Saharan Africa where the ongoing HIV/AIDS pandemic leads to higher prevalence of cryptococcosis.
 
Combination of amphotericin and flucytosine (5-FC) is the mainstay of therapy for the initial management of CM. Indeed, it has even been shown that effective delivery of these therapies in sub-Saharan Africa can lower mortality rates by 90%. However, even while 5-FC is included on the WHO list of essential medicines, its availability world-wide is limited. Since 5-FC has few clinical indications, it is not manufactured widely, leading to high costs for the medication, and limited distribution in sub-Saharan Africa.
 
While early studies of 5-FC in CM were done in the pre-AIDS era, the dose of 150 mg/kg/day was selected and resulted in significant toxicities, including leukopenia and thrombocytopenia requiring dose reduction or discontinuation of 5-FC. Later retrospective studies of dosing in the AIDS era were inconclusive about the ideal dose to benefit efficacy and toxicity. In 1997, van der Horst performed the first major clinical trial for AIDS related CM demonstrating efficacy of combination of 5-FC with amphotericin B. The selected dose was 100 mg/kg/day, which has been used as standard dosing ever since. Optimizing dose necessary for good clinical outcomes could reduce the daily dose and increase the total number of patients able to be treated at the same cost and supply. In our own studies of Cryptococcus in Uganda, the MIC₅₀ is approximately 4-8 mg/L. Preliminary models of dosing based on AMBITION pharmacokinetics of 5-FC has shown that lower doses may still be acceptable at targets of 40% or 60% time over MIC.

	
Results: *hypothetical* flucytosine probability of target attainment
 
%T>MIC: TARGET IS NOT KNOWN
 
ICCC 2023 Population Pharmacokinetics from AMBITION-cm

Description of Study Intervention:	
Standard dosing for 5-FC is 100 mg/kg/day divided in 4 doses over waking hours for 7-14 days during the period of induction therapy. We will deliver doses of:
 
 1. 60mg/kg/day in 3 divided doses for 10 days 
This most commonly will be 2 500mg tablets three times per day

Prelim Data	
Molloy et al. demonstrated in the ACTA trial published in 2018 that 1 week of IV Amphotericin B 1 mg/kg plus oral 5-FC 100 mg/kg is the optimal management for the first week of CM. These are shown to have benefits in mortality and similar rates of fungal clearance from the CSF to other combination regimens.

Phase II Study Design	
Prospective, open-label trial to compare the efficacy and safety of lower doses of 5FC during induction therapy to historical controls with standard 5FC dosing.
 
 1. Participants in the trial will receive 60mg/kg/day of 5-FC in 3 divided doses for 10 days, n=36 2. Single-dose liposomal amphotericin (10mg/kg) is preferred, if available. 3. Amphotericin B 0.7-1.0 mg/kg/day may be used if needed. 4. Historical controls drawn from the AMBITION trial will be used as a comparison group, selected weighted by inclusion/exclusion criteria, baseline characteristics and therapies received. Induction therapy for control group participants followed the 2018 WHO cryptococcal guidelines with 7 days of 5-FC 100mg/kg/day and 7 days of IV Amphotericin deoxycholate followed by 1200mg fluconazole/day for 7 days. The intervention group received single-dose liposomal amphotericin plus 5-FC and fluconazole 1200 mg/day.

	
All participants will receive fluconazole 1200mg/day during consolidation therapy from day 1 to 14 then 800mg/day from day 15 to 10 weeks, and 200mg/day after 10 weeks.
 
All participants will receive lumbar punctures at diagnosis, day 3, day 5-7, day 10-14, and additionally as required for control of intracranial pressure and documentation of CSF sterilization. Controls from Ambition will be matched for the same LP windows. Therapeutic LPs conducted during the first week have a ~70% relative survival benefit.

Phase II Study Endpoints	
Primary:
 
 1. Rate of CSF Cryptococcus clearance (Early Fungicidal Activity, or EFA), quantified by the change of \log_{10} Cryptococcus CFU/mL CSF/day as measured by serial quantitative CSF fungal cultures over ~2 weeks 
Secondary:
 
 1. CSF culture sterility cumulative incidence over 18 weeks 2. 18-week survival time 
Key Secondary:
 
 1. Desirability of Outcome Response (DOOR) as ordinal ranked maximum score tested by Win Ratio. 
 a. 18-week Survival with CSF sterility by 2-weeks b. 18-week survival with CSF culture positivity beyond 2 weeks c. Grade 3 hematological adverse event by 2 weeks d. Grade 4 hematological adverse event by 2 weeks e. Lost to follow up before 18-weeks f. Serious Adverse Event through 18 weeks (e.g. all-cause re-hospitalization, permanent neurologic deficit) g. Death by 18-weeks 
Safety & Exploratory:
 
 1. Incidence of Grade 3-5 Laboratory abnormalities over 2 weeks 2. Incidence of Clinical Grade 3-5 Adverse Events or Serious Adverse Events (SAEs) over 2 weeks 3. Pharmacokinetics of 5FC in blood, CSF, and bodily fluids / tissues.
Phase II Duration:	18 weeks
Phase II Number of Participants	36 CSF culture positive participants with an EFA estimate With adaptive sample size up to 50 CSF CrAg+ participants consented
Phase II Inclusion Criteria	
 ● CSF cryptococcal antigen (CrAg) positive meningitis ● Ability and willingness to provide informed consent ● Willing to receive protocol-specified lumbar punctures

Phase II x Criteria	
 • Age < 18 years • Inability to take enteral (oral or nasogastric) medicine • Cannot or unlikely to attend regular clinic visits • Receiving chemotherapy or corticosteroids • Suspected Paradoxical immune reconstitution inflammatory syndrome (IRIS) • Pregnancy or breastfeeding • CrCl < 20 mL/minute • Absolute neutrophil count < 500 x10⁶ cells/L • Thrombocytopenia < 50,000 x 10⁶ cells/L • Patients with prior 5-flucytosine exposure >3 days in the 12 months prior to enrollment • Any condition for which participation would not be in the best interest of the participant or that could limit protocol specified assessments.
Phase II Study Drug and Dosing	
 • Participants will receive 5-FC 60mg/kg/day for 10 days. • Participants will receive IV AMB 0.7-1.0 mg/kg/day for 7 days. • Liposomal Amphotericin B single IV dose 10 mg/kg is preferred, when available. • All participants will receive fluconazole 1200 mg/day during consolidation therapy from day 1 to 14 then 800 mg/day from day 15 to 10 weeks, and 200mg/day after 10 weeks.
Phase II Monitoring	
 • All participants will have CSF quantitative fungal cultures performed on Days 1, 2-4, 5-7, and 10-14 of antifungal treatment. • 3x weekly CBC, chemistries, and kidney function tests for duration of induction therapy during hospitalization
Phase II Safety Analysis	
The Data Monitoring Committee (DMC) will conduct interim safety analysis after 10 participants are enrolled with >2 weeks of accrued data and calculable EFA.
 
EFA and culture positive Cryptococcus relapse will be monitored by the trial investigators, and if statistical evidence shows that EFA <0.2 log₁₀ CFU/mL/day, then an early DMC will be called.

Phase II Statistical Design Rationale	
Early fungicidal activity (EFA) is a quantitative measure of antimicrobial activity for an antifungal regimen in human patients with cryptococcal meningitis. In numerous trials, EFA correlates well with 10-week mortality. Specifically, EFAs worse than 0.20 log₁₀ CFU/mL/day are associated with higher mortality (>50%) and EFA better than 0.3 log₁₀ CFU/mL/day is associated with lower mortality (30-40%).
 
EFA is calculated by measuring the slope of the clearance rate of yeast from CSF, which is calculated from longitudinal quantitative CSF cultures collected over two weeks.
 
By intent to treat analysis, all participants who are enrolled in this study will be included for analysis.

Clinical Trial Sites	
 1. Mulago Hospital, Kampala, Uganda 2. Kiruddu Hospital, Kampala, Uganda 3. Mbarara Regional Referral Hospital, Mbarara, Uganda

Estimated Time to Complete Enrollment:	Up to 12 months
---	-----------------

Table of Contents

1. KEY ROLES	1
2. BACKGROUND AND SCIENTIFIC RATIONALE	2
2.1 Background Summary and Study Hypotheses	2
2.2 Burden of Cryptococcal Meningitis	2
2.3 Treatment of Cryptococcal Meningitis	4
2.4 Rationale for Optimizing 5FC Dose	6
2.5 Early Fungicidal Activity	7
2.6 Potential Risks and Benefits	10
3. OBJECTIVES	12
3.1 Study Objectives	12

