7. PHASE II TRIAL STUDY SCHEDULE

7.1 Schedule of Events

	Scree ning	Enr oll me nt	Da y 3	Da y 5- 7	Day 1 0- 1 4	Wee k 4	We ek 6	We ek 8	We ek 1 0	We ek 1 2	We ek 1 8	Pre ma ture Disc onti nuat ion
Procedures												
Signed Consent Form		X										
Assess Eligibility Criteria	X	X										
Review of Medical History	X	X										
Enrollment		X										
Assess Clinical Status		X	X	X	X	X	X	X	X	X	X	X
Assess Adverse Event		X	X	X	X	X	X					X
Na, K, creatinine	X	X		X	X			X				
CBC	X	X		X	X			X				
CD4		X										
CD4		X										
ALT, T-bilirubin		X						X				
CSF Collection & Storage	X		X	X	± ¹	± ²						
Urine Pregnancy Test	X											
Re se arc h La bs	Storage of Blood for PK and research studies		X ³									
	ART Initiation/Change						X					
	Quantitative Neurocognitive									X		

¹ Day 14 CSF can be collected between days 10-14. If CSF cultures are sterile from ≥ 7 days prior (i.e. culture obtained on day 3 is sterile on day 10), lumbar punctures may be deferred at Day 14. Participants may be discharged from the hospital after 7 days, if ambulatory and clinically stable.

² If CSF culture is positive at Day 14 then an LP must be performed at Week 4. For those who remain culture positive thereafter, follow up LPs should be conducted as per best practices to document sterility.

³ Optional: Peripheral blood mononuclear cells (PBMCs) – Kampala only (optional)

All study visits have an allowable visit window of ± 1 day for Day 3-7 visit, ± 2 days from Day 7-14 visits, and 4 Weeks and beyond have ± 1 week visit window.

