7.3 Hospital Follow-up Visits

Hospital follow up visits have a visit window, as defined below, to accommodate weekends and/or holidays when the local laboratories are closed. Participants will generally be seen by a study investigator daily during hospitalization recording administration of study medicine, antifungal medicines, and additional IV fluids.

Follow up Visits

Day ~3

A study medical officer will assess between day 2-4:

- Interval history occurring since the prior study visit
- Vital signs
- Focused physical and neurologic examination, directed by symptoms
- Medications and adherence (as appropriate)
- Adverse events (AEs)

Laboratory monitoring will include, at a minimum:

- Serum creatinine
- Serum chemistry (Na, K)
- Lumbar puncture with quantitative fungal culture
- Storage of plasma, serum, and CSF.

Day 5-7

A study medical officer will assess during day 5-7:

- Interval history
- Vital signs
- Focused physical and neurologic examination, directed by symptoms
- Medications and adherence (as appropriate)

- Adverse events (AEs)

Laboratory monitoring will include, at a minimum:

- CBC with autodiff
- Lumbar puncture with CSF quantitative culture
- Storage of plasma, serum, and CSF.
- Optional: Peripheral blood mononuclear cells (PBMCs) – Kampala only (optional)
- Optional: Intensive PK sampling of peripheral blood with samples taken 1, 2, 4, 7, 12, and 23 hours after the first dose of 5-FC that day

Participants can be discharged from the hospital after day 7 if they are fully ambulatory and their clinical condition has been deemed stable by the study medical officer, but return for a Day 14 outpatient study visit.

Day 10 - 14

A study medical officer will assess between day 8-14:

- Interval history
- Vital signs
- Focused physical and neurologic examination, directed by symptoms
- Medications and adherence (as appropriate)
- Adverse events (AEs)

Laboratory monitoring will include, at a minimum:

- Serum creatinine
- Serum chemistry (Na, K)
- CBC with autodiff
- \pm Lumbar puncture with CSF quantitative culture (at physician discretion, see below*)
- Storage of plasma, serum, and CSF.

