* A lumbar puncture at Day 10-14 is at physician discretion, based on earlier quantitative culture results. If participants have sterile cultures from ≥ 7 days prior (i.e. Day 3 or Day 5-7 CSF culture, respectively) AND have an absence of ongoing symptoms of elevated intracranial pressure (e.g. headache), then physicians may opt to not perform the lumbar puncture.

If life-threatening (Grade 4) lab abnormalities are present or develop during the course of the study, laboratory monitoring shall occur with greater frequency for subject safety. Example:

- Creatinine: if values > 3 mg/dL (>265 mmol/L), Creatinine will be repeated at least daily until stable
- Potassium: if values ≤ 2.5 mEq/L or ≥ 6.5 mEq/L potassium will be repeated STAT and at least daily until improving

In the event of a prolonged hospitalization, the study team will continue to follow the patient daily in the hospital, with assessments, evaluation, and monitoring undertaken according to expected routine standards of care. If any subject is hospitalized at the time of their expected clinic follow-up visit (Week 4, 6, 8, or 10), the study visit will occur while hospitalized.

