8.3.1 Hematology

CBC monitoring will be encouraged as part of routine care at the start of induction antifungal therapy, initial evaluation for ART, and whenever clinically indicated. Scheduled draws will occur at enrollment, Day 5-7, Day 14, and Week 6.

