11.6 Safety and Exploratory Endpoints

- 1) Laboratory anomalies (Grade 3-5 AEs) as per the NIAID DAIDS toxicity grading table will be summarized for the incidence over 2 weeks of having at least one event and the mean number of events with cumulative incidence and linear regression models, respectively. If the cumulative incidence of a laboratory AE for any given anomaly (e.g. anemia, acute kidney injury) is >10%, the lab measurement will be individually summarized as a continuous variable. This is the key safety endpoint.
 - a) Grade 1-2 AEs will also be collected and summarized but are not the protocol scientific endpoint.
- 2) Clinical adverse events (Grade 3-5 AEs or SAEs) will be summarized via cumulative incidence function.
 - a) Note: Clinical AEs are listed separately from laboratory anomalies as lab AEs occur in the majority of this critically ill population with advanced AIDS and receiving IV AMB.
- 3) Tolerability will be assessed as the percent of received and tolerated doses versus total daily doses as a continuous variable for the experimental low-dose 5-FC and control standard dose 5-FC groups over the first two weeks.
 - a) Dropouts and study withdrawals will be summarized.
- 4) Descriptive analyses for the lower-dose 5-FC on pharmacokinetics of 5-FC concentrations in blood, CSF, and other bodily fluids/tissues; both antemortem and possibly postmortem.

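### Blood tests are three times weekly in the synopsis but twice after enrolment in Sections 7.1, 7.3 and 8.3.1, and no lab-window rule is stated for comparing draw-dependent toxicity endpoints with AMBITION controls

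*Combined protocol and SAP*

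**What the plan says.** **Frequency of testing.** The synopsis (Phase II Monitoring) calls for "3x weekly CBC, chemistries, and kidney function tests for duration of induction therapy during hospitalization". Section 8.3.1 states: "Scheduled draws will occur at enrollment, Day 5-7, Day 14, and Week 6". It also says that "CBC monitoring will be encouraged as part of routine care at the start of induction antifungal therapy" and permits further counts when clinically indicated. Section 7.3 introduces its visit lists with "Laboratory monitoring will include, at a minimum", and lists a CBC at Day 5-7 and Day 10-14 but not at Day 3. The table in 7.1 agrees on those two visits. A footnote to 7.1 adds: "Participants may be discharged from the hospital after 7 days, if ambulatory and clinically stable". After a Grade 4 laboratory value, 7.3 says that "laboratory monitoring shall occur with greater frequency for subject safety".

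**Endpoints.** Section 11.6 names Grade 3-5 laboratory abnormalities over two weeks as the key safety endpoint. It summarises the incidence of one or more events and the mean number of events "with cumulative incidence and linear regression models, respectively". Section 9.2.1 derives laboratory events by grading values in the database. DOOR ranks c and d (11.5) are Grade 3 and Grade 4 haematological events by two weeks.

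**Comparison.** Section 11.3 hypothesises less toxicity than with standard-dose 5-FC, and Section 4.1 takes the comparison group from AMBITION. On timing, the synopsis (Phase II Study Design) says: "Controls from Ambition will be matched for the same LP windows". No equivalent sentence covers blood tests.

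**The concern.** An abnormality that falls between draws is never graded and never counted. Both summaries in 11.6, and the chance of being placed in DOOR rank c or d, therefore depend on how often blood is taken as well as on toxicity. If the two cohorts were sampled at different intensities, the comparison would mix toxicity with ascertainment.

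Three features add to this:

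- Sites that follow different sections of the protocol would sample differently.
- The three-times-weekly rule ends at discharge, and discharge requires being ambulatory and stable, so sicker participants are tested more.
- Testing increases after a Grade 4 value, and no rule says whether repeated abnormal values are one event or several. The mean event count can then grow because of the first event.

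At stake are the reduced-toxicity hypothesis and the key secondary endpoint.

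**Working it through.** The plan gives no event rate, sample size or power for these endpoints, so there is no figure to reproduce.

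**Step 1: post-enrolment CBCs in two weeks.**

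- Synopsis, full two-week stay: 3 × 2 = 6.
- Synopsis, discharge after day 7: 3 in week 1 plus the Day 10-14 visit = 4.
- Sections 7.1, 7.3 and 8.3.1: Day 5-7 and Day 10-14 (Day 14 in 8.3.1) = 2.

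The texts differ 2- to 3-fold (4/2 to 6/2), before any extra draws.

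**Step 2: dependence on draws.** Suppose each draw independently has a 10% chance of a Grade 3-5 value (an assumption). P(one or more) = 1 − 0.9^k, and the mean count is 0.1k.

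- k = 2: 19.0%, mean 0.2
- k = 4: 34.4%, mean 0.4
- k = 6: 46.9%, mean 0.6

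**Step 3: episode model.** Let onset be uniform over Days 0-14 and let an episode last L days. A draw on day d detects onsets between d − L and d. The detected share is the union of these intervals within 0-14, divided by 14. The assumed draw days are 6, 14 (two draws); 2, 4, 6, 14 (four); and 2, 4, 6, 9, 11, 13 (six).

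| L | 2 draws | 4 draws | 6 draws | Ratio 4:2 | Ratio 6:2 |
|---|---|---|---|---|---|
| 3 days | 6/14 = 43% | 9/14 = 64% | 13/14 = 93% | 1.5 | 2.2 |
| 5 days | 10/14 = 71% | 11/14 = 79% | 13/14 = 93% | 1.1 | 1.3 |
| 7 days | 13/14 = 93% | 13/14 = 93% | 13/14 = 93% | 1.0 | 1.0 |

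As a check, the onset range was changed to Days 1-14 and the draw days to 2, 4, 7, 14 and 2, 4, 7, 9, 11, 14, still against 6, 14. The shares for 2/4/6 draws become 46/69/100% (3 days), 77/85/100% (5 days) and 92/100/100% (7 days). The ratios are almost unchanged.

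**Step 4: what this could do to a comparison.** This step uses the shares from that check. Take 50 trial participants (the enrolment ceiling) and 164 controls (the Ugandan AMBITION intervention arm, Section 4.1). Assume a true incidence of 30% in both and test two-sided at 0.05. The chance of a false difference is Φ((|p1 − p2| − 1.96·SE0)/SE1), where SE0 is the pooled and SE1 the unpooled standard error.

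For 3-day episodes at 6 against 2 draws, p1 = 0.30 and p2 = 0.139. Then SE0 = 0.062 and SE1 = 0.070, and the chance is about 72%. At 4 against 2 draws it is about 24%. For 5-day episodes the two figures are 18% and 5.5%. For 7-day episodes both are about 5%, the nominal level.

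The DOOR win ratio was computed with assumed shares:

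- 3%, 7% and 20% of participants in ranks e, f and g.
- 30% true haematological toxicity in the remaining 70%, split 60:40 between c and d.
- The rest split 70:30 between a and b.

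At 6 against 2 draws and with identical truth, the win ratio is 0.81 (3 days), 0.92 (5 days) and 0.97 (7 days) instead of 1.0.

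**Step 5: direction.** More draws in the trial than in the controls would count more toxicity in the low-dose cohort and bias against it. Fewer would favour it. With the same windows in both cohorts the detected shares are equal and this artefact disappears.

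**The case against.** **A reader might infer that lab windows are not matched to AMBITION.** The documents do not show that. The Document History says the schedule of events was updated to align with the comparator's, and 11.3 defers historical-control methods to a Statistical Analysis Plan. What stands is narrower: no lab-window matching rule is stated in Section 11 or elsewhere in the documents, and the synopsis frequency departs from the visit schedule.

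**A reader might infer a 1.5- to 2.2-fold bias, or a false reduction in toxicity.** Neither follows. Those ratios give the controls two draws and the trial four to six, and the AMBITION laboratory schedule is not available. They also need short episodes. The documents give no durations, and the commonest event in Appendix A is anaemia (88 events, against 54 for neutropenia), with nothing to suggest that it lasts only three days. The illustrated scenario counts against the low dose.

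**The contradiction is partly softened.** The synopsis rule applies only in hospital, the 7.3 lists are minimums, and 8.3.1 allows more counts when indicated. That narrows the gap for early discharges but does not make a fixed three-times-weekly rule equal to two scheduled draws.

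**Inferential weight is limited.** Section 11.1 reserves hypothesis testing for the primary efficacy endpoint, and 11.7 calls secondary endpoints mainly descriptive. This stands for the laboratory summaries. DOOR is the exception, since it is tested by win ratio, though ranks e to g dilute the effect. Early death is a gap for the mean count only, because the one-or-more summary uses cumulative incidence.

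**Conclusion.** The point holds in limited form. The texts contradict each other on blood-test frequency (about 4-6 post-enrolment CBCs against 2). The key safety endpoint and DOOR ranks c and d rise with the number of draws, and no rule equalises laboratory ascertainment with the historical controls.

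The actual bias cannot be sized or signed from the documents. The illustration rests on assumed draw days, uniform onset, assumed episode length and equal true incidence. Under it the artefact is large for abnormalities lasting about three days, modest at five and negligible at a week or more. This should be corrected before the between-cohort analysis. It does not touch the EFA primary endpoint.

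**What to change.** 1. Reconcile the synopsis with 7.1, 7.3 and 8.3.1 into one schedule. This review does not choose the frequency.
2. For between-cohort laboratory comparisons and DOOR ranks c and d, base the main analysis only on post-baseline results in windows confirmed to exist in both cohorts, for example Day 5-7 and Day 10-14. Confirm this from the AMBITION data before the analysis, separately for blood counts and chemistry, and state the window limits. Section 7.3 heads the last hospital visit Day 10-14 but describes assessment from day 8.
3. Use enrolment values as baseline only. Sections 9.1 and 9.9 do not treat pre-existing abnormalities as new events unless they worsen.
4. Count repeated abnormal values of one test within a window once.
5. Add an all-draws sensitivity analysis, and report the number of draws per participant in each cohort.
6. Keep every result in clinical monitoring and the safety listings.

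An offset for the number of draws is not needed. Testing is partly driven by the outcome, so draws are not a neutral exposure, and common windows make the adjustment largely redundant.

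The cost is protocol wording and analysis programming. The downside is that some in-hospital events leave the main comparison, although they remain in the sensitivity analysis and listings.
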